### 6.1.3 Treatment arms/group

Participants will be assigned at the visit on Day 1 for study treatment randomization to one of the following five treatment arms to achieve a ratio of 2:2:2:1:1 at the end of the study. Each participant will begin taking the prescribed regimen consisting of two placebo and one active tablet OR three placebo tablets CCI starting on Day 1 (randomization) and continuing until Part 2B DBPCFC end-of-treatment visit. The CCI dose on the day of Part 2B DBPCFC end-of-treatment visit will be the last dose administered. The CCI dose will not be administered.

1. Remibrutinib CCI every day on Days 1 through 28
2. Remibrutinib CCI every day on Days 1 through 28
3. Remibrutinib CCI every day on Days 1 through 28
4. Placebo CCI every day on Days 1 through 28
5. Placebo CCI every day for Days 1-21, followed by remibrutinib CCI every day on Days 22 through 28

Treatment duration is approximately one month (4-5 weeks). Participants will receive study drug from the site staff at randomization (Day 1), Day 8 and Day 22 visits. Dispensation of study drug by the site to the participants must be recorded. Participants will administer drug at home, except on clinic days. On clinic days, participants should withhold their CCI dose and take it at the instructed time during the visit (based on assessment schedule and PK draws, etc.). If participant has already taken the dose CCI, this should be noted on patient diary and eCRF. If visit includes PK assessments, participant should be rescheduled to the next available clinic day for the PK visit. Participants' compliance with taking study drug must be

recorded in the source documents and the corresponding electronic Case Report Form (eCRF) to document administration. Dosing information may be collected in eCRF for specific visits (e.g.: visits with PK draws). Study drug reconciliation should be performed at each study visit or per the monitoring plan. The follow-up period is a non-treatment period of 30 days after the last dose of study drug during which neither study treatment will be administered nor study assessments will be performed.

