### 1.1 Study design

Figure 1-1 Study Overview

This is a Phase 2 multi-center, randomized, participant- and investigator-blinded, placebo-controlled study to assess the safety and clinical efficacy of four dosing regimens of oral remibrutinib versus placebo (CCI for one month (4-5 weeks); CCI for one month (4-5 weeks); CCI for one month (4-5 weeks); placebo for 3 weeks followed by remibrutinib CCI for 1-2 weeks; and placebo for one month (4-5 weeks) in adult participants with a medically confirmed diagnosis of IgE-mediated peanut allergy. Approximately 72 participants will be randomized in this study to one of the five arms (randomization ratio of 2:2:2:1:1). Participants initially assigned to the 3-week placebo arm will receive the first dose of blinded remibrutinib treatment at the Day 22 visit. CCI. This is operationally handled by stratification to treatment arms based on CCI participation within the IRT system, and hence, not considered as a design parameter or confounding variable. The primary analysis will be conducted after all participants complete the end of study visit schedule.

CCI

CCI

CCI

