

To evaluate the efficacy of oral remibrutinib CCI compared to placebo, as measured by the proportion of participants who can tolerate a single dose of <math>\geq 1000</math> mg (2044 mg cumulative tolerated dose) of peanut protein without dose-limiting symptoms during the DBPCFC at one month

To evaluate the efficacy of oral remibrutinib CCI compared to placebo, as measured by the proportion of participants who can tolerate a single dose of 3000 mg (5044 mg cumulative tolerated dose) of peanut protein without dose-limiting symptoms during the DBPCFC at one month

To evaluate the efficacy of oral remibrutinib CCI compared to placebo, as measured by the maximum symptom severity at any single challenge dose up to and including 1000 mg of peanut protein during the DBPCFC at one month

To evaluate the efficacy of 3 weeks of placebo treatment followed by 1 week of oral remibrutinib CCI treatment compared to one month of placebo treatment, as measured by the proportion of participants who can tolerate a single dose <math>\geq 600</math> mg of peanut protein without dose-limiting symptoms during the DBPCFC at one month

To evaluate the effects of multiple doses of remibrutinib compared to placebo (when applicable), as measured by multiple systemic biomarkers to inform on response to treatment or disease severity

	

Responder status defined as tolerating a single dose of <math>\geq 1000</math> mg (2044 mg cumulative tolerated dose) of peanut protein without dose-limiting symptoms during the DBPCFC conducted at one month

Responder status defined as tolerating a single dose of 3000 mg (5044 mg cumulative tolerated dose) of peanut protein without dose-limiting symptoms during the DBPCFC conducted at one month

Maximum severity of symptoms occurring at any challenge dose of peanut protein up to and including 1000 mg during the DBPCFC conducted at one month. Symptom severity will be categorized as 4 levels: None, Mild, Moderate, Severe

Responder status defined as tolerating a single dose of <math>\geq 600</math> mg (1044 mg cumulative tolerated dose) of peanut protein without dose-limiting symptoms during the DBPCFC conducted at one month (3 weeks of placebo + 1 week of remibrutinib treatment vs. one month of placebo)

Change from baseline at Weeks 1 and 4 of:

peanut-specific IgE, including peanut components

peanut-specific IgG4, including peanut components

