## 2.1.1 General definitions

### 2.1.1.1 Study treatment

In this document, 'study medication', 'study treatment' or 'study drug' will be used to refer to investigational therapy assigned to a participant. Study drug refers to either remibrutinib or placebo.

The treatment arms in this study are as follows.

- Remibrutinib CCI
- Remibrutinib CCI
- Remibrutinib CCI
- Placebo for 3 weeks followed by remibrutinib CCI for 1 week
- Placebo

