The proportion of responders for the allergen dose defined as ordinal categorical variable ranging from 0-3000 mg will be analyzed utilizing the proportional odds model. The model will include treatment arm, log-transformed baseline total IgE, and log-transformed

maximum tolerated allergen dose at baseline. Proportion of responders and 80% CI will be presented for each of the peanut allergen dose challenge administered to the participants.

A Kaplan-Meier plot with responder rate vs. peanut allergen dose after one month or after 1 week of treatment will be presented to show any differences across treatment arms (i.e., remibrutinib doses, placebo).

- Change from baseline in peanut-specific IgE and IgG4 after one week/after one month of treatment: Summary statistics, including geometric means and geometric standard deviations, will be presented for peanut-specific IgE and IgG4 along with changes from baseline by time point and treatment group. Change from baseline in log-transformed levels of peanut specific-IgE and peanut specific-IgG4 after one week/one month of treatment will be analyzed using an ANCOVA model with terms for treatment arm, and log-transformed baseline peanut specific-IgE or peanut specific-IgG4.

Ratio of peanut specific IgE to IgG4 for all participants at baseline and post-baseline will be plotted by treatment arm and the descriptive summaries of this ratio will be reported.

- Responder status defined as tolerating a single dose of  $\geq 600$  mg (1044 mg cumulative tolerated dose) of peanut protein without dose-limiting symptoms during the DBPCFC conducted after one week of treatment (3 weeks of placebo + 1 week of remibrutinib treatment vs. placebo). Proportion of responders and 80% CI over placebo will be presented with the same logistic regression model as defined for the primary analysis.
- Change from baseline in wheal size diameters from SPT after one week/after one month of treatment will be analyzed using ANCOVA with baseline wheal size as a covariate and the change from baseline will also be summarized descriptively. Model adjusted means and 80% confidence intervals will be presented for each of the treatment arms over placebo.

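### Week 1 IgE/IgG4 ANCOVA: the delayed-start arm is still on placebo but is left out of the placebo reference, which costs precision

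*SAP*

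**What the plan says.** **Endpoint.** SAP Table 1-1 (section 1.2) defines the biomarker endpoint as "Change from baseline at Weeks 1 and 4 of" peanut-specific IgE and IgG4, including components. Protocol Table 2-1 agrees. The matching objective is a comparison with placebo, where applicable.

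**Analysis.** The relevant bullet of SAP 2.6.1 is headed "Change from baseline in peanut-specific IgE and IgG4 after one week/after one month of treatment". It says that the log-transformed changes "will be analyzed using an ANCOVA model with terms for treatment arm, and log-transformed baseline peanut specific-IgE or peanut specific-IgG4". Summary statistics are given "along with changes from baseline by time point and treatment group". Protocol 12.5.1 has the same plan.

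**Arms.** SAP 2.1.1.1 lists five arms. One is "Placebo for 3 weeks followed by remibrutinib" for one week, listed separately from Placebo.

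**Timing of the switch.** Protocol 6.1.3 describes that arm as "Placebo CCI every day for Days 1-21", then active drug (the regimen is redacted). SAP 1.1 says: "Participants initially assigned to the 3-week placebo arm will receive the first dose of blinded remibrutinib treatment at the Day 22 visit".

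Neither document has a rule that combines the two placebo-to-date groups at Week 1. SAP 2.7 does separate the placebo and remibrutinib periods of the delayed-start arm, but only for adverse event listings.

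**The concern.** At calendar Week 1 the placebo and delayed-start arms have had the same treatment. Both took blinded placebo, matched in appearance and schedule (Protocol 6.5), and both were randomised concurrently. A five-level treatment factor ignores this. Each one-month dose is then compared with a reference mean built from the placebo arm alone, although the trial has twice as many concurrent placebo participants at that visit.

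A five-level factor also allows four contrasts with placebo at Week 1. The fourth, delayed-start versus placebo, compares placebo with placebo and carries no information about remibrutinib.

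The stake is precision on one time point of a named secondary endpoint. Placebo data are scarce in this 2:2:2:1:1 design. For the primary endpoint, SAP 2.5.5 goes as far as borrowing historical placebo data in a supplementary analysis. The extra Week 1 placebo participants are already in the trial and need no assumption about exchangeability with other trials.

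**Working it through.** **Inputs**
- N = 72, ratio 2:2:2:1:1 (SAP 1.1; Protocol 3).
- Discontinuation about 10%; completers 14 to 16 per one-month arm and 7 to 8 in each of the other two arms (Protocol 12.8).
- First remibrutinib in the delayed-start arm on Day 22 (SAP 1.1).
- The documents give no SD or expected effect for IgE/IgG4, so results are in SD units.

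**Step 1. Reproduce the plan's arm sizes.**
- One-month arms: 72 × 2/8 = 18. Placebo and delayed-start: 72 × 1/8 = 9 each.
- At 10% loss: 18 × 0.9 = 16.2 and 9 × 0.9 = 8.1. These match the upper ends of the stated ranges.
- The lower ends (14 and 7) imply 1 − 14/18 = 1 − 7/9 = 22% loss.
- Week 1 comes before most dropout, so 18/9 and 14/7 should bracket the number with Week 1 data.

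**Step 2. Placebo-only participants at Week 1.** 9 + 9 = 18. The placebo level of the five-arm model uses 9 of them, one half.

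**Step 3. SE of a dose-versus-placebo difference.** SE = SD × √(1/n_dose + 1/n_ref).

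| n_dose v n_ref, five arms | SE (SD units) | n_dose v n_ref, pooled | SE (SD units) | Ratio |
|---|---|---|---|---|
| 18 v 9 | √(1/18 + 1/9) = 0.408 | 18 v 18 | √(1/18 + 1/18) = 0.333 | 0.816 |
| 16 v 8 | 0.433 | 16 v 16 | 0.354 | 0.816 |
| 14 v 7 | 0.463 | 14 v 14 | 0.378 | 0.816 |

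The SE falls by 1 − 0.816 = 18.4%, and the variance by 1 − 0.816² = one third. Read the other way, the unpooled SE is 1/0.816 = 1.225 times the pooled one.

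**Step 4. Equivalent sample size.** Keeping 2:1 and scaling both groups by k divides the variance by k. Matching the pooled variance needs k = 1/0.816² = 1.5, which is 50% more participants in that comparison. Pooling achieves it by raising the comparison from 27 to 36 people (18 + 9 to 18 + 18), because it also balances the groups.

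**Step 5. Check with the ANCOVA itself.** In 4,000 simulated trials per setting, with five arms and then four groups and a baseline covariate, the mean model SE fell from 0.409 to 0.334 (18/9) and from 0.464 to 0.381 (14/7). This agrees with the formula.

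**Step 6. Illustrative power.** Standardised effects are assumed. One-sided 10% is borrowed from the primary test, since the plan states no level for this endpoint.

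| Assumed effect (SD) | 18 v 9 | 18 v 18 | 14 v 7 | 14 v 14 |
|---|---|---|---|---|
| 0.5 | 48% | 59% | 42% | 52% |
| 0.8 | 75% | 87% | 67% | 80% |
| 1.0 | 88% | 96% | 81% | 91% |

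**The case against.** **The phrase may not mean calendar Week 1.** This is the strongest counter-argument. Elsewhere in SAP 2.6.1, one week of treatment means three weeks of placebo plus one week of remibrutinib, assessed at one month. The 600 mg responder bullet says so outright, and the tolerated-dose text must mean it, since the only post-baseline food challenge is at end of treatment. On that reading the IgE/IgG4 ANCOVA has no Week 1 comparison and the point falls away. But both endpoint tables name Weeks 1 and 4 for IgE/IgG4, and the bullet summarises by time point, so calendar Week 1 is the better reading. The treatment-period rows of Protocol Table 8-1 that would confirm Day 8 sampling were not legible in the copy used. The need to state which meaning applies stands either way.

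**The contrasts are inferred.** The IgE/IgG4 bullet does not spell out comparisons over placebo, as the SPT bullet does, and nothing forbids pooling. That is correct. The comparison comes from the objective, and the separate levels come from the arm list and the absence of a pooling rule.

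**The arm's name is transparent.** It says that placebo comes first, so a careful reader could see that the Week 1 row is a placebo row. That reduces the risk of misreading but recovers no precision.

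**Pooling is not entirely free.** The reference group would differ between Week 1 and Week 4. This stands as a small cost. The randomisation was also stratified on a redacted item, which SAP 1.1 says is not a confounder; pooling relies on that statement.

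**Stronger readings that the documents do not support.** A reader might infer that half the placebo controls are thrown away. They are not: delayed-start participants stay in the model and inform the residual variance and the baseline slope, and only the reference mean omits them. A reader might also infer a biased or invalid analysis, but analysing by arm is valid. Nor does the point extend to SPT, whose endpoint is at one month (Table 1-1) even though its bullet uses the same one-week wording.

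**Conclusion.** The point holds as a matter of efficiency at one time point. With calendar Week 1 as the time point and a five-level arm factor, the SE of each one-month dose versus placebo is about 22% larger than it needs to be; pooling removes 18% of it. This ratio depends only on the 2:1 allocation and is the same for randomised numbers and for the stated completers. The absolute gain in power cannot be given, because the plan states no SD or effect for IgE/IgG4.

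The conclusion rests on two readings: that one week in this bullet means calendar Week 1, and that treatment arm means the five arms of SAP 2.1.1.1.

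The primary MCP-Mod analysis, which excludes the one-week regimen from the dose-response fit, and the choice of dose from it are unaffected. The change is worth making because it is a specific gain at almost no cost, using data already collected.

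**What to change.** In SAP 2.6.1, for the IgE/IgG4 bullet only:

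- State that one week means calendar Week 1, in line with Table 1-1.
- For Week 1, replace the five-level arm factor with a treatment-to-date factor of four levels: the three one-month doses, and placebo to date (placebo and delayed-start arms combined) as reference. Drop the delayed-start versus placebo contrast at that time point.
- Keep all five arms at one month, and leave the SPT analysis as it is.
- Add a footnote to the tables that the Week 1 and Week 4 reference groups differ, and record the rule in SAP section 4, which now reports no changes from the protocol's analyses.

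The cost is a sentence or two, one derived variable and the footnote. No new data or visits are needed. The rule should be dated before the final database lock.

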## 2.7 Safety analyses

For all safety analyses, the safety set will be used. All listings will be presented by treatment group and tables will be presented by treatment arm and overall. For the 3 weeks Placebo followed by remibrutinib CCI for 1 week arm, the AEs will be listed by the placebo period and remibrutinib period separately to differentiate the AEs that occurred during the respective period.

Safety summaries (tables, figures) will include only data from the on-treatment period with the exception of baseline data from Screening Visits 1, 2 and 3 which will also be summarized where appropriate (e.g. change from screening summaries). In addition, a separate summary for death including on treatment and post treatment deaths will be provided. In particular, summary tables for AEs will summarize only on-treatment events, with a start date during the on-treatment period.

The on-treatment period lasts from the date of first administration of study treatment (Day 1) to 28 days after the end of treatment.

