## 12.5.2 Safety endpoints

For all safety analyses, the safety set will be used. All listings will be presented by treatment group and tables will be presented by treatment arm and overall.

Safety summaries (tables, figures) will include only data from the on-treatment period with the exception of pre-dosing data from Screening Visits 1, 2 and 3 which will also be summarized where appropriate (e.g. change from screening summaries). In addition, a separate summary for death including on treatment and post treatment deaths will be provided. In particular, summary tables for adverse events (AEs) will summarize only on-treatment events, with a start date during the on-treatment period (treatment-emergent AEs).

The on-treatment period lasts from the date of first administration of study treatment (Day 1) to end of treatment.

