### 12.5.2.1 Adverse Events

All adverse events summarized will be displayed by treatment group and overall. All adverse events listings will be presented by treatment arm and participant.

All events that the investigator classifies as reactions associated to the DBPCFC or SPT must be captured on the designated eCRF and will not be reported on the AE eCRF. These events will be reported separately and not included in reporting of treatment-emergent AEs.

The number (and percentage) of participants with treatment emergent adverse events (events started after the first dose of study medication or events present prior to start of double-blind treatment but increased in severity based on preferred term) will be summarized in the following ways:

1. by treatment, primary system organ class and preferred term
2. by treatment, primary system organ class, preferred term and maximum severity
3. by treatment, Standardized MedDRA Query (SMQ) and preferred term

Separate summaries will be provided for study medication related adverse events, death, serious adverse events, and other significant adverse events leading to discontinuation. In case of sparse events in any of these categories occur, only a listing will be provided if deemed adequate.

Adverse events of special interest for remibrutinib treatment CCI will also be summarized for all participants.

A participant with multiple adverse events within a primary system organ class is only counted once towards the total of the primary system organ class.

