
Objective(s)	Endpoint(s)

To evaluate the safety and tolerability of multiple doses of remibrutinib

To assess the ability of remibrutinib to impact skin mast cells through the assessment of allergen-specific skin prick test (SPT)

To assess the pharmacokinetics (PK) of remibrutinib

	

Treatment-emergent adverse events, vital signs, ECG, and laboratory values, including immunoglobulin levels

Change from screening in SPT mean wheal diameters at one month

Remibrutinib concentrations in blood and PK parameters (including, but not necessarily limited to: Cmax, AUClast, AUCtau, Tmax)

Exploratory objective(s)	Endpoint(s) for exploratory objective(s)
CCI	

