### 2.7.1 Adverse events (AEs)

All AEs summarized will be displayed by treatment group and overall. All AEs listings will be presented by treatment arm and participant.

All events that the investigator classifies as reactions associated to the DBPCFC or SPT must be captured on the designated eCRF and will not be reported on the AE eCRF. These events will be reported separately and not included in reporting of treatment-emergent AEs (events started after the first dose of study medication or events present prior to start of treatment but increased in severity based on preferred term).

The number (and percentage) of participants with treatment emergent AEs will be summarized in the following ways:

1. by treatment, primary system organ class and preferred term
2. by treatment, primary system organ class, preferred term and maximum severity
3. by treatment, Standardized MedDRA Query (SMQ) and preferred term

Separate summaries will be provided for study medication related AEs, death, serious adverse events (SAEs), and other significant AEs leading to discontinuation. In case of sparse events in any of these categories occur, only a listing will be provided if deemed adequate.

A participant with multiple AEs within a primary system organ class is only counted once towards the total of the primary system organ class.

For the legal requirements of clinicaltrials.gov, two required tables on treatment-emergent AEs which are not SAEs with an incidence greater than a certain threshold based on the final database and on treatment-emergent SAEs and SAEs suspected to be related to study treatment will be provided by system organ class and PT on the safety set population.

If for a same patient, several consecutive AEs (irrespective of study treatment causality, seriousness and severity) occurred with the same SOC and PT:

- a. a single occurrence will be counted if there is  $\leq 1$  day gap between the end date of the preceding AE and the start date of the consecutive AE
- b. more than one occurrence will be counted if there is  $> 1$  day gap between the end date of the preceding AE and the start date of the consecutive AE

For occurrence, the presence of at least one SAE / SAE suspected to be related to study treatment / non SAE has to be checked in a block e.g., among AE's in a  $\leq 1$  day gap block, if at least one SAE is occurring, then one occurrence is calculated for that SAE.

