#### **2.7.1.1 Adverse events of special interest / grouping of AEs**

AEs of special interest (AESI) are defined in the latest version of the compound electronic Case Retrieval Strategy (eCRS). The classification reflects the safety topics of interest identified in the current version of the remibrutinib Development Safety Profiling Plan, and may be updated based on review of accumulating data. The number and percentage of participants with treatment emergent AEs of special interest will be summarized by risk category, PT and treatment.

The Compound Case Retrieval Strategy (CRS) will be used to determine the MedDRA search criteria to be used to identify events of special interest. The most recent list of adverse events

of special interest at the time of database lock will be used. CCI

- CCI
- CCI
- CCI

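### SAP 2.7 filters adverse-event tables by start date, which removes the pre-existing events worsening on treatment that SAP 2.7.1 says the same tables count (minor)

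*SAP*

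**What the plan says.** Treatment-emergent AEs are part of a named secondary endpoint. SAP Table 1-1 lists "Treatment-emergent adverse events, vital signs, ECG, and laboratory values, including immunoglobulin levels" against the safety and tolerability objective.

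Two adjacent SAP sections state what enters the AE tables.

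- **SAP 2.7** sets a filter: "summary tables for AEs will summarize only on-treatment events, with a start date during the on-treatment period". It then fixes the window: "The on-treatment period lasts from the date of first administration of study treatment (Day 1) to 28 days after the end of treatment".
- **SAP 2.7.1** specifies the tables: "The number (and percentage) of participants with treatment emergent AEs will be summarized in the following ways". Its definition of a treatment-emergent AE has two limbs. One is onset after the first dose. The other is "events present prior to start of treatment but increased in severity based on preferred term".

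SAP 2.7.1.1 carries the same term into the special-interest tables: "The number and percentage of participants with treatment emergent AEs of special interest will be summarized by risk category, PT and treatment".

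The protocol splits in the same place. Section 12.5.2 restricts AE tables to events "with a start date during the on-treatment period (treatment-emergent AEs", and so equates that start-date condition with treatment emergence. Section 12.5.2.1 adds "events present prior to start of double-blind treatment but increased in severity based on preferred term".

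**The concern.** An event already present before treatment has, on its own record, a start date before Day 1. The SAP 2.7 filter therefore removes exactly the events that the second limb of the SAP 2.7.1 definition brings in. The two sections cannot both be followed. Either the worsening limb never takes effect, or the word *only* in SAP 2.7 is untrue.

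The AE incidence reported by arm would then depend on which section the programmer implements. This reaches the main AE tables, the special-interest tables and the registry tables described in SAP 2.7.1, all of which rest on the treatment-emergent term. It does not touch the primary or any other efficacy analysis.

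**Working it through.** There is no stated figure to reproduce. The check is to apply both rules to each kind of AE record.

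**Rule A** (SAP 2.7): start date from Day 1 to 28 days after end of treatment.
**Rule B** (SAP 2.7.1): started after first dose, or present before treatment and later more severe. No upper time limit is written.

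| Case | Rule A | Rule B |
|---|---|---|
| 1. Starts before Day 1, never worsens | out | out |
| 2. Starts before Day 1, worsens after first dose, same record | **out** | **in** |
| 3. Starts after first dose, within 28 days of end of treatment | in | in |
| 4. Starts more than 28 days after end of treatment | **out** | **in** |

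Case 2 is the substantive conflict.

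**Can case 2 records exist?**

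- Protocol 10.1.2 counts AEs from informed consent. Protocol Table 8-1 places Screening Visit 1 between Day -30 and Day -15 and collects AEs at all three screening visits.
- Protocol 10.1.2 has each AE followed to resolution, with its severity reassessed at every visit.
- The date-imputation rules in SAP 5.1.2 provide for AEs that began before treatment.
- No section tells sites to open a new record, with a new start date, when severity increases.
- SAP 2.7.1 has a rule for consecutive records of the same preferred term regardless of severity. It hints that a severity change might be split into separate records. But it governs occurrence counts, merges records no more than one day apart, and gives no onset date to a worsening.

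**Case 4** is a minor gap. Protocol 10.1.2 continues AE monitoring for at least 30 days after the last dose, and Table 8-1 sets the safety call at 30 ± 5 days. Taking end of treatment as the last dose, the call falls no later than day 30 + 5 = 35, which is at most 35 − 28 = 7 days past the SAP 2.7 window.

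**Weight of one participant.** With 72 randomised 2:2:2:1:1, the ratio parts sum to 8.

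- Each one-month remibrutinib arm: 72 × 2/8 = 18, so 1/18 = 5.6 percentage points.
- Placebo arm and delayed-start arm: 72 × 1/8 = 9 each, so 1/9 = 11.1 percentage points.

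These figures are the weight of any single participant. They do not estimate how many case 2 events will occur.

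**The case against.** The strongest reply is that case 2 is rare and its consequences limited. Most of that stands.

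- **Co-morbid allergic disease.** A reader might infer that worsening asthma, rhinitis or atopic dermatitis would be lost. The documents do not support this. Protocol 10.1.2 sends conditions present at consent to medical history, so they have no AE record before dosing. If one worsens on drug and is reported as an AE, that record would normally start in the window and pass the filter.
- **Screening challenges.** A reader might also look to the screening food challenges. Reactions attributed to the challenge or the skin prick test go on a separate form and are kept out of treatment-emergent reporting (Protocol 12.5.2.1, SAP 2.7.1). Protocol 16.4.6 keeps challenge reactions off the AE form unless serious. The exclusion is not absolute, because Protocol 10.1.1 treats severe dose-limiting symptoms as AEs, but this is a weak source.
- **A hidden signal.** This reading is too strong. SAP 2.7 confines summaries, not listings, to the on-treatment period, and SAP 2.7.1 provides AE listings by arm and participant.
- **Two SAP definitions.** SAP 2.7 does not define treatment-emergent AEs. It filters tables, and the only SAP definition is in 2.7.1. It is Protocol 12.5.2 that attaches the term to the start-date condition.

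It could also be argued that the specific section, 2.7.1, should override the general one. Neither document says so, and the *only* in SAP 2.7 points the other way. Nor can the conflict be dismissed as a question of data entry, since no rule requires a worsening to be recorded as a new event.

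**Conclusion.** The conflict holds on the text of both documents. It affects descriptive tables for a named secondary endpoint, and nothing resolves it. Severity is minor.

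What remains is mainly an AE unrelated to the challenges that begins between consent and Day 1, persists past the first dose and then worsens on the same record. The likely number is small and cannot be computed from the documents. It is zero if no such event occurs or if every worsening is entered as a new dated record, and there is no loss from the tables if the programmer follows SAP 2.7.1. Where such an event does occur and the start-date filter is applied, a table row changes by 5.6 or 11.1 points, and only if that participant has no other qualifying event in the row.

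The conclusion assumes the planned arm sizes of 18 and 9, and that a worsening may stay on its existing record, which the documents permit but do not state. The rest of the SAP suggests worsening was meant to count: SAP 2.7.3 tabulates new or worsening laboratory abnormalities, and SAP Table 2-7 does the same for notable vital signs.

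**What to change.** Before database lock:

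1. In SAP 2.7, replace the start-date condition by: *with onset, or an increase in severity over the pre-dose severity of the same preferred term, during the on-treatment period*.
2. Bound the SAP 2.7.1 definition by the same on-treatment window, which also closes case 4.
3. Derive one treatment-emergent flag from this rule and use it for all AE, SAE and AESI tables.
4. Record in the SAP how Protocol 12.5.2 and 12.5.2.1 are to be read together, as SAP 2.2 already does for the conflict over the efficacy analysis set.

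The documents do not show whether the eCRF dates a severity change within a record. If it does not, either have each worsening entered as a new dated AE record, or flag an event when its maximum on-treatment severity exceeds its pre-dose severity.

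The cost is a short SAP edit and a small derivation or data-entry step. Reported AE incidence may rise slightly.
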